### **Other Safety Analyses**

PE findings and weight measured throughout the trial will be reported using descriptive statistics.

### **Exploratory Analyses**

Metabolites of HPG1860 may be reported. The correlation of PK values and study outcomes may be explored, specifically the correlation between PK concentration measures and LFC.

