### Primary Objectives and Endpoints

Objective	Endpoint

To investigate the safety and tolerability profile of HPG1860 3 mg, 5 mg, and 8 mg versus placebo in subjects with nonalcoholic steatohepatitis (NASH).

	
Primary Safety Endpoint
 
Safety and tolerability of 12 -week treatment of HPG1860 3 mg, 5 mg, and 8 mg in subjects with NASH as assessed by:
 

Treatment-emergent adverse events (TEAEs)

Adverse events of special interest (AESI)

Serious adverse events (SAEs)

Changes in clinical safety laboratory values

Vital signs

Electrocardiogram (ECG)

To evaluate the efficacy of HPG1860 compared to placebo.

	
Key Secondary Efficacy Endpoint
 

Change from baseline (CFB) in liver fat content (LFC) measured by magnetic resonance

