**Exploratory Objectives and Endpoints**

	cholesterol (TC), and apolipoprotein B (apoB) at Weeks 2, 4, 8, 12, and 16. Note: HDL-C, LDL-C, and triglycerides (TG) will be measured as clinical safety laboratory assessments

 
To collect reserve samples for future evaluation of the effect of HPG1860 compared to placebo on additional biomarkers, not otherwise described
 
To characterize HPG1860 metabolites
 
To characterize the relationship between PK values and study outcomes
 
	
 
Assess biomarkers, not otherwise described, acquired from reserve samples
 
To measure HPG1860 metabolites
 
Explore correlations between PK concentration and LFC
 

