**Study Design:**

This is a Phase 2a, randomized, double-blind, placebo-controlled, parallel group, multiple arm, multicenter study of 3 different doses of HPG1860 versus placebo in subjects with biopsy-confirmed or phenotypic NASH. Screening will occur up to 5 weeks prior to randomization; all eligible subjects will have baseline hepatic imaging during Screening, prior to randomization. Approximately 80 eligible subjects will be randomized 1:1:1:1 on Day 1/Week 0 (T1) to receive either HPG1860 3 mg (n = 20), or 5 mg (n = 20), or 8 mg (n = 20), or placebo (n = 20) for 12 weeks. Following a preplanned interim analysis, a dose cohort may be dropped and/or added.

Randomized subjects will return for clinic visits at Week 2 (T2), Week 4 (T3), Week 8 (T4), and Week 12 (T5) as well as Week 16 (T6). Imaging procedures will be completed during Screening, Week 4 (T3), and Week 12 (T5). A follow-up visit will be completed 4 weeks after last dose of investigational medicinal product (IMP) at Week 16 (Visit T6).

At selected PK sites, serial PK samples will be collected from approximately 6 to 8 subjects in each dose cohort; blood samples will be collected on Day 1 pre-dose (within 30 minutes prior to dosing) and at 1, 2, 4, 6, and 8 hours ( $\pm 15$  minutes) post-dosing and on Day 14 pre-dose (within 30 minutes before dosing) and at 1, 2, 4, 6, and 8 hours ( $\pm 15$  minutes) post-dosing, and at 24 hours

(±30 minutes) prior to dosing on Day 15.

For all subjects, PK samples will be taken within 30 minutes prior to dosing at Weeks 4, 8, 12, and 16.

This study includes collection of reserve samples at Baseline (Day 1) and Week 12 for future biomarker analysis, unless prohibited by local law or regulations, and where approved by the Institutional Review Board (IRB).

**Duration of  
Treatment:**

Total study duration per subject: 21 weeks (approximate)

Screening: up to 5 weeks

Treatment: 12 weeks

Follow-up: 4 weeks

**Planned Sample Size  
and Treatment  
Groups:**

Planned: Approximately 80 adult male and female subjects

HPG1860 3 mg (n=20)

HPG1860 5 mg (n = 20)

HPG1860 8 mg (n = 20)

Placebo (n = 20)

Following a preplanned unblinded (comparative) interim analysis when 50% of randomized subjects have reached the Week 12 endpoint, an ongoing treatment group (3 mg, 5 mg, or 8 mg) may be dropped and/or a new treatment group of dose may be added.

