### **Statistical Procedures:**

#### **Sample Size**

A sample size of 17 in each group will provide 90% power to detect an absolute difference in mean CFB of 7.0% (a 33% reduction from baseline assuming a percent LFC value of 21.5% at baseline and 14.5% at Week 12) in at least 1 of the HPG1860 treatment groups compared to placebo using Dunnett's multiple comparisons test with a 2-sided significance level of 0.05 and assuming a common standard deviation of 6.8%. To account for a 15% dropout rate, approximately 20 subjects per group will be randomized.

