### **Key Secondary Efficacy Analysis**

The change in LFC measured by MRI-- PDFF from baseline to Week 12 will be analyzed using analysis of covariance (ANCOVA) adjusted for baseline LFC and treatment group. To control for multiple comparisons, Dunnett's test will be used to test if any of the treatment groups are significantly different from the placebo group.

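### The exploratory exposure-response analysis is worded as an unadjusted correlation of concentration with LFC; it should use change in LFC, adjusted for baseline LFC and body weight

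*Combined protocol and SAP*

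**What the plan says.** The objective, under Exploratory Objectives and Endpoints, is "To characterize the relationship between PK values and study outcomes". Its endpoint is "Explore correlations between PK concentration and LFC". The statistical text under Exploratory Analyses reads "The correlation of PK values and study outcomes may be explored, specifically the correlation between PK concentration measures and LFC". None of the three names change from baseline, a baseline term, a body-size covariate, the visit, the exposure metric, the type of correlation, or the handling of dose groups and placebo.

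The efficacy text differs. The key secondary endpoint is "Change from baseline (CFB) in liver fat content (LFC) measured by magnetic resonance" imaging at Week 12, and its analysis "will be analyzed using analysis of covariance (ANCOVA) adjusted for baseline LFC and treatment group". The Week 4 endpoint is also a change, and the responder endpoint is a percent reduction from baseline.

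On data, Study Design states: "For all subjects, PK samples will be taken within 30 minutes prior to dosing at Weeks 4, 8, 12, and 16". MRI-PDFF is done at Screening, Week 4 and Week 12, and weight is listed under Other Safety Measures. Serial PK is limited to about 6 to 8 subjects per dose cohort.

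**The concern.** A subject's LFC at Week 4 or 12 is baseline plus change. Inclusion criterion 7 sets a floor of 10% and Sample Size assumes a mean of 21.5%, so a wide baseline spread is plausible. That spread is noise when the question is whether exposure drives response.

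Dose is randomised, but concentration within a dose is not. If, for example, heavier subjects have lower concentrations and more liver fat, concentration and LFC are correlated before any drug is given.

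At stake is the answer to a stated exploratory objective of a three-dose study: a real relation could be missed, or a spurious one reported. Because the variable, visit and metric are left open, they could also be chosen after unblinding.

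**Working it through.** **Plan's own figure.** The plan gives no figure for this analysis. Its sample-size statement supplies the SD and n used below, so it was checked first: "A sample size of 17 in each group will provide 90% power to detect an absolute difference in mean CFB of 7.0" percentage points "in at least 1 of the HPG1860 treatment groups compared to placebo using Dunnett's multiple comparisons test", SD 6.8, two-sided 0.05. A simulated Dunnett test with all three doses effective gives 90.8% power at n = 17 (88.9% at 16), and 17/0.85 = 20. The figure reproduces with 6.8 read as the SD of change. Active completers: 3 × 17 = 51.

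**Weakening of a true relation.** Let W = B + C (Week 12 LFC = baseline + change), with exposure X independent of B.

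- r(X,W) = r(X,C) × SD_C / SD_W
- SD_W² = SD_B² + SD_C² + 2 r_BC SD_B SD_C
- Baseline-adjusted r = r(X,C) / √(1 − r_BC²)
- Power ≈ Φ(√(n − 3) × atanh|r| − 1.96), n = 51

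From the plan: SD_C = 6.8. Assumed: r(X,C) = -0.40, SD_B 5 to 8, r_BC 0 to -0.5. Power with change is 84% in every row.

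| SD_B | r_BC | SD_W | r with level | Power, level | Power, baseline-adjusted |
|---|---|---|---|---|---|
| 5 | 0 | 8.44 | -0.32 | 64% | 84% |
| 8 | 0 | 10.50 | -0.26 | 45% | 84% |
| 6.5 | -0.3 | 7.87 | -0.35 | 70% | 87% |
| 8 | -0.5 | 7.47 | -0.36 | 75% | 93% |
| 5 | -0.5 | 6.10 | -0.45 | 91% | 93% |

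Level loses to change only when SD_W > 6.8, that is when SD_B > −2 r_BC × 6.8. The last row fails that condition (5 < 6.8), and level then does better than change. Baseline adjustment is at least as good as either throughout.

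**False relation, moderate assumptions.** No exposure effect. Assumed: size-exposure correlation a = -0.3 to -0.5, size-baseline LFC correlation b = 0.2 to 0.4, change independent of baseline. The spurious r with level is a × b × SD_B / √(SD_B² + 6.8²):

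- low: -0.3 × 0.2 × 5/8.44 = -0.04
- high: -0.5 × 0.4 × 8/10.50 = -0.15

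Simulated two-sided false-positive rates at n = 51 are 6% to 19% for level and 5% for change. If size also correlates 0.2 to 0.4 with change, the change score itself gives 7% to 30%. If change correlates with baseline, unadjusted change picks up a × b × r_BC, for example -0.5 × 0.4 × -0.5 = +0.10.

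**False relation, stronger assumptions.** Simulation with 17 subjects at each of 3, 5 and 8 mg, baseline mean 21.5 and SD 7.4, log-ratio SD 0.30, within-dose log-exposure SD 0.5, no exposure effect. Log exposure falls by 0.15 or 0.30 per SD of baseline log LFC.

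| Slope | Level | Absolute change | Log change | Baseline-adjusted |
|---|---|---|---|---|
| 0.15 | 19% | 11% | 5% | 5% |
| 0.30 | 55% | 24% | 5% | 5% |

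The 0.30 slope implies a within-dose exposure-baseline correlation of -0.30/√(0.30² + 0.5²) = -0.51. If body size is the only link, that needs two correlations of about 0.7 each, so it is an extreme case.

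With an assumed Emax effect and no body-size link (mean Spearman correlation -0.25 with level, -0.36 with log change), power was about 43% for level, 62% for absolute change, 75% for log change and 78% for baseline-adjusted regression.

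**The case against.** The strongest reply is that LFC here is shorthand. The sentence and the objective both speak of outcomes of the study, and every LFC outcome in the document is a change or a percent reduction. Efficacy Criteria for Evaluation itself uses liver fat content as a bare label and then explains it as change from baseline. The text is also a synopsis, where a one-line exploratory item would not normally list covariates. This stands in part: a reader might infer that the plan deliberately chose level over change, but the wording leaves the variable open. It does not settle the matter, because a plain correlation with absolute change still performs worse than a baseline-adjusted model (62% against 78% power; 11% to 24% against about 5% false positives).

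Second, the analysis is optional and plans no test, alpha or decision rule, so power and error rates are only a yardstick for comparing methods. That stands and limits the weight of the point. A reader might also infer that the result feeds dose choice. The documents do not say so: the interim dropping or adding of a dose group is not linked to any PK correlation.

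Third, the body-size link is assumed, and randomised dose drives part of the exposure variation when doses are pooled. That stands too.

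**Conclusion.** The point holds as a low-cost improvement to an exploratory analysis. As worded, the correlation ignores baseline LFC and body size. Compared with using change, the effect on power runs from no loss to roughly half (84% down to 45%). The false-positive rate is about 6% to 19% under moderate confounding and about 55% in an extreme case. These figures rest on assumed baseline SDs, baseline-change correlations and body-size links; only n, the SD of 6.8, the doses and the mean LFC come from the plan.

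Two stronger readings are not supported. One is that baseline LFC necessarily hides a true relation: level can do as well as change when the baseline SD is small and change correlates negatively with baseline. The other is that switching to change cures confounding: it does not if body size also affects response. The sample size and the key secondary analysis are unaffected.

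**What to change.** In both the exploratory endpoint and the Exploratory Analyses text, define the outcome as change in LFC from baseline at Weeks 4 and 12, preferably relative change or log-ratio. Relate it to C_trough at the same visit, in subjects on active drug, by regression adjusted for baseline LFC and body weight. State how the dose groups are pooled.

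Placebo subjects need not be included. Zero exposure cannot enter on the log scale, and a plain drug-versus-placebo difference could produce a slope even when response does not vary with concentration among treated subjects. Use this at most as a sensitivity analysis.

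The cost is wording and a little analysis time: pre-dose samples, MRI-PDFF and weight are already collected. C_trough is the practical metric, because serial PK covers only 18 to 24 active subjects (3 × 6 to 3 × 8), where a correlation of -0.40 has about 38% to 49% power. Within-dose exposure remains non-randomised, so the report should call the result observational.
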